2.1.5.3 Laboratory safety variables

Clinical laboratory data consists of blood analysis, including hematology, clinical chemistry, and urinalysis. Clinical laboratory values after conversion will be analyzed into standard international units and international units will be used in all listings and tables.

Blood samples for clinical laboratories will be taken at Visit 1 (Screening), Visit 2 (Day 1), Visit 4 (Week 4), Visit 5 (Week 8), Visit 6 (Week 12), Visit 7/EOT (Week 24), early termination and Visit 8/EOS (Week 35) unless otherwise specified. The laboratory parameters will be classified as follows:

- Hematology
 - **Red blood cells and platelets and coagulation:** Hemoglobin, hematocrit, red blood cell count, erythrocyte sedimentation rate (ESR) and platelet count,
 - **White blood cells:** white blood cell count with differential blood count (neutrophils, lymphocytes, monocytes, basophils, eosinophils),
 - **Tuberculosis screen:** a Quantiferon®-TB gold evaluation.
- Biochemistry
 - **Metabolism:** Fasting glucose, total protein, albumin, high-sensitivity C-reactive protein (hsCRP),
 - **Electrolytes:** sodium, potassium, chloride, calcium, phosphorous, bicarbonate,
 - **Renal function:** serum creatinine, creatinine phosphokinase (CPK), blood urea nitrogen, clearance of creatinine according to Cockcroft and Gault formula (mL per minute) (qualitative variable: <30, [30-50[, [50-80], >80),
 - **Pregnancy test:** (For women of childbearing potential) β-HCG blood test and urine pregnancy tests will be performed,
 - **Liver function:** alkaline phosphate (ALP), Alanine transaminase (ALT), Aspartate transaminase (AST), total bilirubine (TBILI),
 - [REDACTED]
- Serology
 - **Hepatitis screen:** hepatitis B surface antigen, hepatitis B surface antibody, HBV DNA, hepatitis C antibody, hepatitis C RNA, HIV-1/HIV-2 antibody,
 - [REDACTED]
- Urine sample
 - **Urinalysis** (by dipstick): specific gravity, pH, glucose, ketones, occult blood, protein, nitrate, leukocyte esterase, urobilinogen and bilirubin.

Technical formulas are described in [Section 2.5.1](#).

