2.4.5 Analyses of safety data

The summary of safety results will be presented by treatment group.

General common rules

All safety analyses will be performed on the safety population as defined in [Section 2.3.2](#), unless otherwise specified, using the following common rules:

- Safety data in patients who do not belong to the safety population (eg, exposed but not randomized) will be listed separately.
- The baseline value is defined as the last available value before the first administration of the IMP.
- The potentially clinically significant abnormality (PCSA) values are defined as abnormal values considered medically important by the Sponsor according to predefined criteria/thresholds based on literature review and defined by the Sponsor for clinical laboratory tests, vital signs, and ECG (PCSA version dated May 2014 [[Appendix A](#)]).

- PCSA criteria will determine which patients had at least 1 PCSA during the TEAE period, taking into account all evaluations performed during the TEAE period, including unscheduled or repeated evaluations. The number of all such patients will be the numerator for the treatment-emergent PCSA percentage.
- The treatment-emergent PCSA denominator by group for a given parameter will be based on the number of patients assessed for that given parameter in the TEAE period by treatment group on the safety population.
- For quantitative safety parameters based on central laboratory/reading measurements, descriptive statistics will be used to summarize results and change from baseline values by visit (baseline and post-baseline time points) and treatment group. Summaries will include the last and the worst on-treatment value. Only data sampled before or on the day of the last IMP administration will be included in the analysis. The worst on-treatment value is defined as the nadir and/or the peak post-baseline before or on the day of the last IMP administration according to the direction (minimum or maximum) of the abnormality as defined in the PCSA list.
- All measurements (scheduled or unscheduled) will be assigned to time points according to analysis windows as defined in [Section 2.5.4](#).
- The analysis of the safety variables will be essentially descriptive and no systematic testing is planned. Relative risks versus placebo and their 95% confidence intervals may be provided, if relevant.

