2.4.5.3 Analyses of laboratory variables

The summary statistics (including number, mean, median, standard deviation, minimum and maximum) of all laboratory variables (central laboratory values and changes from baseline) will be calculated for each visit (baseline and post-baseline time points) and presented by treatment group. This section will be organized by biological function as specified in [Section 2.1.5.3](#).

For parameters creatinine, glucose, neutrophils, monocytes, basophils, eosinophils and bicarbonate, the last on-treatment and worst on-treatment value will also be provided.

The incidence of PCSAs (list provided in [Appendix A](#)) at any time during the TEAE period will be summarized by biological function and treatment group whatever the baseline level and/or according to the following baseline status categories:

- Normal/missing.
- Abnormal according to PCSA criterion or criteria.

For parameters for which no PCSA criteria are defined, similar table(s) using the normal range will be provided.

Listing will be provided with flags indicating the out of range values as well as PCSA values.

Drug-induced liver injury

The liver function tests, namely AST, ALT, alkaline phosphatase, and total bilirubin, are used to assess possible drug-induced liver toxicity. The proportion of patients with PCSA values at any post-baseline visit by baseline status will be displayed by treatment group for each parameter.

A graph of distribution of peak values of ALT versus peak values of total bilirubin will also be presented. Note that the ALT and total bilirubin values are presented on a logarithmic scale. The graph will be divided into 4 quadrants with a vertical line corresponding to $3 \times \text{ULN}$ for ALT and a horizontal line corresponding to $2 \times \text{ULN}$ for total bilirubin.

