Appendix A Potentially clinically significant abnormalities criteria

CRITERIA for POTENTIALLY CLINICALLY SIGNIFICANT ABNORMALITIES for Phase 2/3 studies (oncology excepted)

Parameter	PCSA	Comments
Clinical Chemistry		
ALT	By distribution analysis: >3 ULN >5 ULN >10 ULN >20 ULN	Enzymes activities must be expressed in ULN, not in IU/L. Concept paper on DILI - FDA draft Guidance Oct 2007. Internal DILI WG Oct 2008. Categories are cumulative. First row is mandatory. Rows following one mentioning zero can be deleted.
AST	By distribution analysis: >3 ULN >5 ULN >10 ULN >20 ULN	Enzymes activities must be expressed in ULN, not in IU/L. Concept paper on DILI - FDA draft Guidance Oct 2007. Internal DILI WG Oct 2008. Categories are cumulative. First row is mandatory. Rows following one mentioning zero can be deleted.
Alkaline Phosphatase	>1.5 ULN	Enzymes activities must be expressed in ULN, not in IU/L. Concept paper on DILI - FDA draft Guidance Oct 2007. Internal DILI WG Oct 2008.
Total Bilirubin	>1.5 ULN >2 ULN	Must be expressed in ULN, not in μ mol/L or mg/L. Categories are cumulative. Concept paper on DILI - FDA draft Guidance Oct 2007. Internal DILI WG Oct 2008.
Conjugated Bilirubin	>35% Total Bilirubin and TBILI>1.5 ULN	Conjugated bilirubin dosed on a case-by-case basis.
ALT and Total Bilirubin	ALT >3 ULN and TBILI >2 ULN	Concept paper on DILI - FDA draft Guidance Oct 2007. Internal DILI WG Oct 2008. To be counted within a same treatment phase, whatever the interval between measurement.

**CRITERIA for POTENTIALLY CLINICALLY SIGNIFICANT ABNORMALITIES
for Phase 2/3 studies (oncology excepted)**

Parameter	PCSA	Comments
CPK	>3 ULN >10 ULN	FDA Feb 2005. Am J Cardiol April 2006. Categories are cumulative. First row is mandatory. Rows following one mentioning zero can be deleted.
CLcr (mL/min) (Estimated creatinine clearance based on the Cokcroft-Gault equation)	<15 (end stage renal disease) ≥15 - <30 (severe decrease in GFR) ≥30 - <60 (moderate decrease in GFR) ≥60 - <90 (mild decrease in GFR) ≥90 (normal GFR)	FDA draft Guidance 2010. Pharmacokinetics in patients with impaired renal function-study design, data analysis, and impact on dosing and labeling.

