eGFR (mL/min/1.73m ²) (Estimate of GFR based on an MDRD equation)	<15 (end stage renal disease) ≥15 - <30 (severe decrease in GFR) ≥30 - <60 (moderate decrease in GFR) ≥60 - <90 (mild decrease in GFR) ≥90 (normal GFR)	FDA draft Guidance 2010. Pharmacokinetics in patients with impaired renal function-study design, data analysis, and impact on dosing and labeling.
Creatinine	≥150 µmol/L (Adults) ≥30% change from baseline ≥100% change from baseline	Benichou C., 1994.
Uric Acid		Harrison- Principles of internal Medicine 17 th Ed., 2008.
Hyperuricemia	>408 µmol/L	
Hypouricemia	<120 µmol/L	
Blood Urea Nitrogen	≥17 mmol/L	
Chloride	<80 mmol/L ≥115 mmol/L	
Sodium	≤129 mmol/L ≥160 mmol/L	
Potassium	<3 mmol/L ≥5.5 mmol/L	FDA Feb 2005.
Total Cholesterol	≥7.74 mmol/L	Threshold for therapeutic intervention.
Triglycerides	≥4.6 mmol/L	Threshold for therapeutic intervention.
Lipasemia	≥3 ULN	

**CRITERIA for POTENTIALLY CLINICALLY SIGNIFICANT ABNORMALITIES
for Phase 2/3 studies (oncology excepted)**

Parameter	PCSA	Comments
Amylasemia	≥ 3 ULN	
Glucose		
Hypoglycaemia	≤ 3.9 mmol/L and $< LLN$	ADA May 2005.
Hyperglycaemia	≥ 11.1 mmol/L (unfasted); ≥ 7 mmol/L (fasted)	ADA Jan 2008.
HbA1c	$>8\%$	
Albumin	≤ 25 g/L	
CRP	>2 ULN or >10 mg/L (if ULN not provided)	FDA Sept 2005.
Hematology		
WBC	<3.0 Giga/L (Non-Black); <2.0 Giga/L (Black)	Increase in WBC: not relevant.
	≥ 16.0 Giga/L	To be interpreted only if no differential count available.
Lymphocytes	>4.0 Giga/L	
Neutrophils	<1.5 Giga/L (Non-Black); <1.0 Giga/L (Black)	International Consensus meeting on drug-induced blood cytopenias, 1991.
		FDA criteria.
Monocytes	>0.7 Giga/L	
Basophils	>0.1 Giga/L	
Eosinophils	>0.5 Giga/L or $>ULN$ (if $ULN \geq 0.5$ Giga/L)	Harrison- Principles of internal Medicine 17 th Ed., 2008.
Hemoglobin	≤ 115 g/L (Male); ≤ 95 g/L (Female)	Criteria based upon decrease from baseline are more relevant than based on absolute value. Other categories for decrease from baseline can be used (≥ 30 g/L, ≥ 40 g/L, ≥ 50 g/L).
	≥ 185 g/L (Male); ≥ 165 g/L (Female)	
	Decrease from Baseline ≥ 20 g/L	
Hematocrit	≤ 0.37 v/v (Male) ; ≤ 0.32 v/v (Female)	
	≥ 0.55 v/v (Male) ; ≥ 0.5 v/v (Female)	
RBC	≥ 6 Tera/L	Unless specifically required for particular drug development, the analysis is redundant with that of Hb. Otherwise, consider FDA criteria.
Platelets	<100 Giga/L	International Consensus meeting on drug-induced blood cytopenias, 1991.
	≥ 700 Giga/L	

**CRITERIA for POTENTIALLY CLINICALLY SIGNIFICANT ABNORMALITIES

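### The creatinine-clearance PCSA bands in SAP Appendix A cover every value, normal ones included, so the CLcr PCSA count and its baseline split cannot isolate a decline in CLcr

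*SAP*

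**What the plan says.** Four parts of the SAP bear on this.

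- **Definition and counting (Section 2.4.5).** PCSAs are abnormal values regarded as medically important. The numerator rule is "PCSA criteria will determine which patients had at least 1 PCSA during the TEAE period", using all evaluations in that period, unscheduled and repeat ones included. For the denominator, "The treatment-emergent PCSA denominator by group for a given parameter will be based on the number of patients assessed for that given parameter".
- **Criteria (Appendix A).** The PCSA column for Cockcroft-Gault CLcr reads "<15 (end stage renal disease) ≥15 - <30 (severe decrease in GFR) ≥30 - <60 (moderate decrease in GFR") and continues "≥60 - <90 (mild decrease in GFR) ≥90 (normal GFR"). A second row, described as "Estimate of GFR based on an MDRD equation", repeats the same five bands. The ALT, AST, total bilirubin and CPK rows state that their categories are cumulative. The CLcr and eGFR rows carry no counting rule.
- **Presentation (Section 2.4.5.3).** PCSA incidence is summarised by arm, overall and/or by baseline status. One baseline stratum is normal or missing; the other is "Abnormal according to PCSA criterion or criteria". Listings flag PCSA values.
- **Variable definition (Section 2.1.5.3).** This section gives other categories: "clearance of creatinine according to Cockcroft and Gault formula (mL per minute) (qualitative variable: <30, [30-50[, [50-80], >80").

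**The concern.** A PCSA criterion has to separate values of concern from the rest. A set of bands that includes the normal range does not, and the rules built on it inherit the problem: the incidence count, the baseline status and the listing flag. The baseline split is the part meant to show whether an abnormality is new on treatment, so its failure matters most.

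Renal function is of interest here. Acute renal failure is an AESI, and renal manifestations are among the exploratory objectives. A CLcr table that shows the same figure in both arms whatever the drug does, or that counts recovery as an abnormality, would be uninformative or misleading for that parameter. The two sets of cut-points add a further ambiguity about which one governs the CLcr output.

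**Working it through.** The documents state no incidence for CLcr, so there is no figure to reproduce. The check applies the written rules.

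**1. Coverage.** With v in mL/min, the Appendix A rule is PCSA(v) = 1 if v < 15, or 15 ≤ v < 30, or 30 ≤ v < 60, or 60 ≤ v < 90, or v ≥ 90. I assigned each of the 3,000 values from 0 to 299.9 in steps of 0.1 to these bands. Each value falls in exactly one band, so PCSA(v) = 1 for every v.

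**2. Bands pooled.** The numerator equals the denominator in each arm. With 47 patients assessed per arm this is 47/47 against 47/47, a ratio of 1.0. At baseline every measured value meets a criterion, so the normal-or-missing stratum holds only patients with no baseline value.

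**3. Bands read one at a time.** Each band now acts as its own criterion, and baseline status is judged against it. Three chosen examples:

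| Baseline CLcr | On-treatment CLcr | Direction | Band newly met |
|---|---|---|---|
| 95 | 80 | decline | 60 to <90 |
| 45 | 75 | improvement | 60 to <90 |
| 80 | 95 | improvement | ≥90 |

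The first two patients are indistinguishable in the 60 to <90 row: neither met that band at baseline, and both meet it on treatment. The third is a new PCSA because the value became normal. All evaluations count and no worst-band rule is given, so one patient can also enter several bands.

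**4. What a lower threshold would show.** Assume worst-value counts from the lowest band to the highest of 1, 4, 10, 14, 18 on active and 0, 0, 4, 15, 28 on placebo. These are illustrative and not from the documents.

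- Any of the five bands: 47/47 (100%) against 47/47 (100%).
- Below 90: 29/47 (61.7%) against 19/47 (40.4%), ratio 1.53.
- Below 60: 15/47 (31.9%) against 4/47 (8.5%), ratio 3.75.

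The data can carry a difference; the all-band count removes it.

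**5. Whether other renal criteria still respond.** The formula in SAP Section 2.5.1 is CLcr = (140 − age) × weight / (0.814 × creatinine), times 0.85 for women. For an assumed woman aged 50, weighing 65 kg, with creatinine 70 µmol/L: 90 × 65 × 0.85 / (0.814 × 70) = 87.3 mL/min. At fixed age and weight CLcr varies inversely with creatinine, so a 30% creatinine rise gives 87.3 / 1.3 = 67.1 and a doubling gives 43.6. The Appendix A creatinine row includes "≥30% change from baseline ≥100% change from baseline" as well as an absolute limit of 150 µmol/L. Reading change as a rise, both of these increases are caught there.

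**6. Cut-points side by side.** A CLcr of 85 is in the top category (above 80) in Section 2.1.5.3 but is a mild decrease in Appendix A. A value of 55 is in the 50 to 80 category in one and in the 30 to <60 band in the other.

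**The case against.** The strongest reply is that nobody would pool the bands. They are graded and labelled, no text tells the programmer to combine them, and tabulated by grade they can differ between arms, as step 4 shows. Since PCSAs are defined as abnormal values, a row labelled normal is naturally a reference row. Section 2.4.5.3 also makes the baseline split optional through its and/or wording, and the safety analysis is descriptive.

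Part of this stands. The 100% figure depends on the literal at-least-one count, and a sensible programmer would probably print the bands separately. But the SAP does not say so for this row, and separate printing does not repair the baseline split: step 3 shows improvement counted as a new PCSA.

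A reader might go further and infer that the trial's renal PCSA incidence as a whole cannot show harm. The documents do not support that. Creatinine has its own absolute and percent-change criteria, blood urea nitrogen has a limit of 17 mmol/L, and Section 2.4.5.3 adds the last and worst on-treatment creatinine. Screening excludes creatinine of 150 µmol/L or more, so a later value at that level would usually be new. Acute renal failure as an AESI is selected by a coding list or an e-CRF tick box, and Protocol Section 9.1.4.4 assesses renal function by blood urea nitrogen, creatinine and urinalysis. None of these uses the CLcr bands.

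Nor does the eGFR row deserve weight. Section 2.5.1 gives no derivation for it, and Appendix A is a general list that also includes parameters outside this trial's laboratory panel, such as HbA1c and lipase. It looks like an unused row.

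**Conclusion.** The defect is real but minor. The CLcr criteria class a normal value as a PCSA, against the SAP's own definition. Taken literally, the CLcr PCSA incidence is 100% of assessed patients in each arm and every value is flagged; this follows from the band limits alone and needs no population assumption. Under either reading of the bands, the normal/abnormal baseline split cannot isolate treatment-emergent decline in CLcr. The consequence is limited to the CLcr output, and to eGFR if it is produced. The conclusion that a renal signal remains visible elsewhere rests on the creatinine, blood urea nitrogen and AESI rules being applied as written, with the creatinine percent change read as an increase.

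**What to change.** 1. In Appendix A, mark the band of 90 and above as the normal reference category and not as a PCSA, for CLcr and for eGFR if that row is kept.
2. Present CLcr as a shift table by arm, baseline band against worst (lowest) post-baseline band in the TEAE period, in place of the normal/abnormal split. Each patient then appears once and improvement is not counted as harm.
3. Read that table alongside the existing creatinine percent-change criteria. A fall from 91 to 89 changes band although creatinine rises only about 2% (91/89 = 1.02), while a fall from 89 to 61 stays in one band although creatinine rises about 46% (89/61 = 1.46). The creatinine criterion catches the second.
4. Reconcile the CLcr cut-points in Section 2.1.5.3 with those in Appendix A.

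The cost is a few lines of SAP text and one table, with no new data. It departs slightly from the sponsor's standard PCSA table, and some one-band shifts will occur by chance near a cut-point. How many depends on population values that the documents do not give.

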11.4.3.2 Laboratory data

The summary statistics (including number, mean, median, SD, minimum and maximum) of all laboratory variables (laboratory values and changes from baseline), will be calculated for each visit (baseline and post-baseline time points), last and worst on-treatment value assessed and presented by treatment group. Only data sampled before or on the day of the last IMP administration will be included in this analysis.

The incidence of PCSAs at any time during the TEAE period will be summarized by treatment group whatever the baseline level and/or according to the baseline status.

For laboratory parameters for which PCSA criterion is not defined, similar table(s) using the normal range could be provided.

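### The incidence of low lymphocyte counts is not tabulated by arm: the only lymphocyte PCSA is a high one, and having it removes lymphocytes from the normal-range table

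*SAP*

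**What the plan says.** - **Criterion.** The haematology block of SAP Appendix A has one lymphocyte entry: "Lymphocytes >4.0 Giga/L". In the same block WBC, haemoglobin, haematocrit and platelets have limits in both directions, and neutrophils have a low limit.
- **Normal-range tables.** SAP 2.4.5.3: "For parameters for which no PCSA criteria are defined, similar table(s) using the normal range will be provided". Protocol 11.4.3.2 sets the same condition but makes the table optional: "For laboratory parameters for which PCSA criterion is not defined, similar table(s) using the normal range could be provided".
- **Last and worst values.** SAP 2.4.5 includes these in the summaries of quantitative safety parameters and fixes the direction of the worst value "according to the direction (minimum or maximum) of the abnormality as defined in the PCSA list". SAP 2.4.5.3 then names seven parameters: "For parameters creatinine, glucose, neutrophils, monocytes, basophils, eosinophils and bicarbonate, the last on-treatment and worst on-treatment value will also be provided". Lymphocytes are not among them. Protocol 11.4.3.2 plans last and worst values for all laboratory variables.
- **What lymphocytes do receive.** They belong to the planned differential (SAP 2.1.5.3: "white blood cell count with differential blood count (neutrophils, lymphocytes, monocytes, basophils, eosinophils"). SAP 2.4.5.3 therefore covers them with "The summary statistics (including number, mean, median, standard deviation, minimum and maximum) of all laboratory variables", which "will be calculated for each visit (baseline and post-baseline time points) and presented by treatment group". The same section plans a listing that flags out-of-range values.

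**The concern.** A parameter with no PCSA at all would get a count of patients outside the normal range. Lymphocytes, because they have a PCSA in the high direction, get no count in the low direction. The gap follows from how two written rules combine, so a programmer who follows the SAP exactly will not produce the row.

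Comparing the safety profile with placebo is a secondary objective (Protocol 5.2). The product neutralises IL-4 and IL-13 (Protocol section 4), and stable low-dose cyclophosphamide, azathioprine, methotrexate, mycophenolate and oral corticosteroids are allowed in both arms (Protocol 8.8.2). Exclusion criterion E 23 sets entry limits for neutrophils, platelets and haemoglobin but none for lymphocytes, so some patients may enter with low counts. A tabulation by arm and baseline status would separate that background from change on treatment, and it is not planned.

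**Working it through.** The documents give no figure to reproduce here. The check sets the rules side by side and then asks how far the remaining outputs fill the gap.

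**Step 1: outputs that could show low lymphocytes**

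| Output | Source | Shows low lymphocytes by arm? |
|---|---|---|
| PCSA incidence, TEAE period | SAP 2.4.5.3, Appendix A | No: high criterion only |
| Normal-range table | SAP 2.4.5.3 | No: excluded because a PCSA exists |
| Worst on-treatment value, seven-parameter list | SAP 2.4.5.3 | No: lymphocytes not listed |
| Worst on-treatment value, general rule | SAP 2.4.5 | No: direction follows the PCSA list, so it is the peak |
| By-visit mean, median, SD, minimum, maximum | SAP 2.4.5.3 | Yes, but no count of patients |
| Listing of out-of-range values | SAP 2.4.5.3 | Individual patients only, no count |
| TEAE tables by preferred term | SAP 2.4.5.1 | Only events reported as AEs |
| Low-WBC PCSA | Appendix A | Indirectly: lymphocytes can be low while total WBC stays above the limit |

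On either reading of the worst-value rule, no nadir is summarised.

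**Step 2: time covered.** SAP 2.4.5 restricts the quantitative summaries to samples taken up to the day of the last dose. The last dose is at Week 23 (Protocol 1.2), and blood is drawn at Weeks 4, 8, 12, 24 and 35 (SAP 2.1.5.3). Read literally, a completer's Week 24 sample falls after the cut-off, leaving Weeks 4, 8 and 12. The PCSA table runs to the last dose plus 84 days. The Week 23 dose falls on study day 1 + 23 × 7 = 162, and 162 + 84 = 246, the target day for Week 35 in SAP Table 3. The longer window therefore takes in Week 24, and Week 35 when that visit is within 84 days of the last dose, but for lymphocytes it counts only high values.

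**Step 3: can by-visit means stand in for a count?** All inputs except the arm size are assumptions: lymphocyte SD 0.5 to 0.7 Giga/L, and a fall of 0.8 Giga/L in a fraction f of one arm with none affected in the other.

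- Shift in the difference of means = f × 0.8.
- Standard error of the difference = SD × √(2/47), which is 0.103 at SD 0.5 and 0.144 at SD 0.7.

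| f | Patients affected (f × 47) | Mean shift (Giga/L) | Shift ÷ SE, SD 0.7 to 0.5 |
|---|---|---|---|
| 5% | 2.35 (about 2) | 0.04 | 0.28 to 0.39 |
| 10% | 4.7 (about 5) | 0.08 | 0.55 to 0.78 |
| 20% | 9.4 (about 9) | 0.16 | 1.11 to 1.55 |

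The means are a between-arm comparison, but a weak one for an effect confined to some patients. The by-visit minimum describes a single patient.

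**Step 4: can AE reporting stand in?** Protocol 10.4.3 makes a laboratory abnormality an AE only if it is symptomatic, needs treatment or consultation, leads to a change in study drug, is serious, or is an AE of special interest. The abnormalities with management charts in Protocol 10.4.6 include neutropenia and thrombocytopenia but not lymphopenia. An asymptomatic low count need not reach the AE tables.

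**The case against.** The strongest reply is that lymphocytes are not ignored. Values and changes from baseline are summarised by visit and arm, low values are flagged in listings, and lymphopenia reported as a TEAE is tabulated by arm. That stands. A reader might infer from Appendix A that low lymphocytes are never compared between arms, or that the PCSA table will report 0% in both. Neither is supported: by-visit summaries by arm exist, and the table has no row for low counts, which differs from a false zero.

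A reader might also infer a known hazard. The documents do not support that. Lymphopenia is not among the legible AEs of special interest (one entry is blacked out). In the earlier IPF study infections were the most common AEs, but their incidence was comparable across groups (Protocol section 4). Background immunosuppression is allowed in both randomised arms.

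Appendix A is a sponsor-wide list in which one-direction criteria are common (RBC, albumin and monocytes, for example). The safety analysis is mainly descriptive, a DMC reviews safety, and a below-LLN count could be produced later from data already held. These points limit the importance but do not remove the gap, because a count added afterwards is not pre-specified.

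Finally, the protocol's abbreviations name CD4, CD8 and CD19, and some laboratory text is blacked out, so subset testing may be planned there. Subset tables would not supply a count of patients with low total lymphocytes.

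**Conclusion.** The point holds as a gap in safety reporting. Under the rules as written, no planned table gives the number and percentage of patients with low lymphocytes by arm, and no lymphocyte nadir is summarised. This rests on the wording of Appendix A and of SAP 2.4.5 and 2.4.5.3, not on an assumed rate. It also assumes that no blacked-out text adds a low criterion for total lymphocytes.

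The size in patients cannot be given, because the documents contain no lymphopenia rate. The range of 0.3 to 1.6 standard errors depends on the assumed SD and fall, and shows only that by-visit means are a poor substitute for a count. The primary endpoint, sample size and error rate are not affected. The case for acting is that the change is cheap and improves a comparison named as a secondary objective.

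**What to change.** 1. Amend SAP 2.4.5.3 so that a parameter with a PCSA in one direction only also receives the normal-range table for the other direction. For lymphocytes this gives n (%) below the central laboratory's LLN, by arm and baseline status, over the TEAE period.
2. Add the lymphocyte nadir to the worst-value summary, alongside the peak if that is kept.
3. Reconcile Protocol 11.4.3.2 and SAP 2.4.5 (last and worst values generally) with SAP 2.4.5.3 (seven parameters), and state which applies.

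The data are already collected and out-of-range values are already flagged, so no new test or threshold is needed. The cost is a slightly longer safety table. The general wording in item 1 also adds rows for other one-direction parameters such as neutrophils, RBC and albumin; if that is unwanted, the sentence can be limited to lymphocytes.
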